5.1.3.6. Missing Data Imputation

After the treatment failures and rescue treatment rules are applied, the remaining missing data will be handled as follows for all of the efficacy analyses including the analyses at key visits (eg Week 16) and over time through Week 52:

- Non-responder imputation will be applied for binary efficacy endpoints.
- No imputation will be performed for missing post baseline continuous values. The statistical model (ie, MMRM) will adjust for missing data.

For the analyses related to the time to event endpoints during the withdrawal and retreatment period, missing PASI score after the Week 16 visit will not be imputed and the value will remain as missing after applying treatment failure rules.

For the efficacy analyses that evaluate the efficacy of retreatment or initiation of guselkumab, after the treatment failure rules are applied, no imputation will be performed for missing data following the retreatment or initiation of guselkumab.

For the efficacy analyses through LTE period, no treatment failures and no missing data imputation will be performed, and the analyses will be based on observed data.

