Part 2 of the main study will be an open-label, single-arm study to collect additional efficacy, safety, and PK data for pediatric participants with a continuous weight-based dose regimen of guselkumab at Weeks 0, 4, and q8w thereafter through Week 52. Participants  $\geq 12$  to  $< 18$  years of age will begin enrollment in Part 2 after the reviews of safety and PK data through Week 16 for all participants  $\geq 12$  to  $< 18$  years of age in Part 1a have been completed, and an appropriate body weight-based dose that matches adult exposure has been confirmed, or a revised body weight-based dose has been determined. Enrollment of participants  $\geq 6$  to  $< 12$  years of age into Part 2 will not occur until all participants in Part 1b have completed 16 weeks of treatment and all efficacy data through Week 16 from Part 1 have been evaluated by the sponsor, and all available safety data have been reviewed by an independent DMC. Part 2 will enroll enough additional participants to achieve a total of at least 100 participants exposed to guselkumab (ie, at least 10 participants in Part 2, with the total number dependent on the number of participants randomized in Part 1 who are exposed to guselkumab).

In Part 2 of the main study, participants will be given the option to self-administer or have their caregiver administer study injections at the study site using the appropriate presentation (either a

prefilled syringe (PFS) assembled with the UltraSafe Plus™ Passive Needle Guard (PFS-U) device, designed to deliver a single, fixed dose of **CCI**

Participants must be at least 12 years of age to self-administer study injections. Participants or their caregivers will be trained on proper use of the device(s) and deemed capable, as determined by study staff. Otherwise injections will continue to be performed by study staff.

All participants who complete either Part 1 or Part 2 of the main study through Week 52 will be offered the opportunity to participate in an open-label LTE. Participants will be required to return to the study site every 8 weeks for safety and efficacy assessments in addition to study intervention administration. Additional details on the LTE can be found in Section 8.

Efficacy assessments (IGA, PASI, BSA, CDLQI, and FDLQI) will be performed according to the Schedules of Activities. Serum samples for PK and immunogenicity analyses will be collected at the timepoints shown in the Schedules of Activities.

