**Long-term Extension (From Week 52 until study termination)**

Following completion of the Week 52 visit, participants who have had a beneficial response from guselkumab treatment as determined by the investigator, and are willing to continue guselkumab treatment, may enter the LTE of the study. Participants who decide to participate in the LTE will continue to receive guselkumab at Week 52 and q8w thereafter until one of the following occurs:

- The participant turns 18 years of age and resides in a country where marketing authorization has been granted for guselkumab treatment of plaque psoriasis in adult patients, and have had the opportunity to complete up to 1 year in the LTE.
- Marketing authorization is obtained for guselkumab for treatment of plaque psoriasis for patients  $\geq 6$  to  $< 18$  years of age in the participant's country of residence.
- Marketing authorization is denied for guselkumab for the treatment of plaque psoriasis for patients  $\geq 6$  to  $< 18$  years of age in the participant's country of residence.
- A company decision is made to no longer pursue an indication in plaque psoriasis in the pediatric population ( $\geq 6$  to  $< 18$  years of age) in the participant's country of residence.

Participants in Part 1 who continue in the LTE portion of the study will receive guselkumab as follows:

- Participants withdrawn from guselkumab or placebo at Week 16 who meet loss of response criteria and are retreated with or initiated guselkumab prior to Week 52 and receive guselkumab at Week 48 will not receive study intervention administration at Week 52 and will resume guselkumab administration at Week 60 and q8w thereafter.
- Participants who meet loss of response criteria at Week 48 will receive guselkumab at Weeks 48 and 52 followed by q8w administration beginning at Week 60.
- Participants withdrawn from treatment at Week 16 who have not been retreated with guselkumab prior to Week 52 will receive a weight-based guselkumab dose at Week 52 and q8w thereafter.

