2.4. Analysis Sets

2.4.1. Efficacy Analysis Sets

2.4.1.1. Full Analysis Set

Full Analysis Set for Part 1

The efficacy analysis set for Part 1 of the study will be based upon the Full Analysis Set (FAS) which includes all randomized subjects in Part 1a and Part 1b. In the efficacy analyses, subjects will be analyzed according to their assigned treatment group regardless of their actual treatment received.

Depending on the endpoints, selected secondary efficacy analyses will be performed on subsets of all randomized subjects:

- PASI 90 responders withdrawn from study agent at Week 16
- PASI 90 responders withdrawn from study agent at Week 16 and later retreated with guselkumab
- PASI 90 non-responders at Week 16 who continued guselkumab treatment
- Etanercept subjects who crossed over to receive treatment of guselkumab

Full Analysis Set for Part 2

The efficacy analyses for Part 2 of the study will be based upon the Full Analysis Set which includes all subjects enrolled in Part 2.

Full Analysis Set for LTE

The efficacy analyses for Long Term Extension will be based upon the Full Analysis Set which includes all subjects who entered into the LTE period.

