5.1.3.3. Treatment Failure Rules

A subject who meets one or more treatment failure criteria specified in Section 5.1.3.2 will be considered a treatment failure from that point onward. The baseline values will be used for all directly measured endpoints regardless of the actual measurements. Zero will be assigned to improvement and percent improvement, and non-responder status will be assigned to binary response variables.

Treatment failure is assumed to have occurred at the earlier of the following dates:

- Date of discontinuation (DC) of study treatment due to lack of efficacy or
- Date of discontinuation of study agent due to an AE of worsening of psoriasis or
- Start date of a protocol-prohibited medication/therapy during the study that could improve psoriasis

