5.5.3. Data Handling

For the efficacy analyses in Part 1, data handling rules specified in Section 5.1.3 will be applied to all IGA, PASI, CDLQI, FDLQI, and BSA related analyses.

[figure not shown]
For the efficacy analyses in Part 2, data handling rules specified in Section 5.1.3 except rescue treatment rules will be applied to all efficacy analyses.

For the efficacy analyses in LTE, the data will be summarized based on observed.

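### Long-term extension efficacy is summarised on observed data only, with no treatment-failure rule, so its response rates are selected upward if participants fail during the extension

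*SAP*

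**What the plan says.** **LTE analysis.** SAP 5.1.3.6 states that in the LTE "no treatment failures and no missing data imputation will be performed, and the analyses will be based on observed data". SAP 5.5.3 repeats it: "For the efficacy analyses in LTE, the data will be summarized based on observed". SAP 5.5.2.3 lists PASI and IGA responses, percent PASI improvement and BSA over time, with no sensitivity or supplementary version.

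**Main study.** SAP 5.1.3.2 defines treatment failure as stopping study agent for lack of efficacy or for an adverse event of worsening psoriasis, or starting a prohibited therapy. From that date SAP 5.1.3.3 applies: "Zero will be assigned to improvement and percent improvement, and non-responder status will be assigned to binary response variables". For data still missing, SAP 5.1.3.6 adds: "Non-responder imputation will be applied for binary efficacy endpoints". Analyses after retreatment or initiation of guselkumab keep the failure rule but do not impute.

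**LTE population.** SAP 2.4.1.1 uses the "Full Analysis Set which includes all subjects who entered into the LTE period". On who may enter, Protocol 4.1 says: "All participants who complete either Part 1 or Part 2 of the main study through Week 52 will be offered the opportunity", and SAP 1.2 has the same wording. The Protocol synopsis and Sections 6.1 and 8 describe entry for "participants who have had a beneficial response from guselkumab treatment as determined by the investigator". Protocol 4.1 refers the reader to Section 8 for LTE detail; SAP 1.2 does not.

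**Neighbouring rules.** SAP 5.1.3.5 applies the failure rules to low- to high-potency topical steroids used after Week 20 and makes no LTE exception. Protocol 6.5.5 permits most topicals after Week 52. SAP 5.5.2.3 also summarises retreated participants at Weeks 60 and 84.

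**The concern.** The LTE curves continue the Week 52 results, but the rule for failures changes at the join and the SAP gives no reason.

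There are two routes to upward selection. A participant who stops for lack of efficacy or worsening psoriasis is absent from later visits and so leaves the denominator. A participant who starts a prohibited therapy and stays on study, which Protocol 6.5 and 7.1 allow with the medical monitor's agreement, is counted as observed and may be a responder. Protocol 7.1 makes the first route realistic, because stopping is to be considered for insufficient improvement.

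What is at stake is the reading of durability, and of the Week 60 and Week 84 retreatment summaries, which bear on a stated secondary objective.

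**Working it through.** The documents state no LTE response or dropout rate, so there is no figure to reproduce. All rates below are assumptions.

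**Formula.** Let N be LTE entrants, L those who have left for lack of efficacy or worsening psoriasis, and R responders still observed.

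- Observed rate (SAP 5.1.3.6 and 5.5.3) = R / (N − L)
- Rate under the failure rule (SAP 5.1.3.3) = R / N
- Ratio of the two = N / (N − L), which is 1 when L = 0

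**Illustration: N = 100, 80 responders at entry, no other change.**

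| L | Leavers had lost response: observed vs failure rule | Leavers were non-responders at entry: observed vs failure rule |
|---|---|---|
| 0 | 80.0% vs 80.0% | 80.0% vs 80.0% |
| 5 | 75/95 = 78.9% vs 75.0% | 80/95 = 84.2% vs 80.0% |
| 10 | 70/90 = 77.8% vs 70.0% | 80/90 = 88.9% vs 80.0% |
| 20 | 60/80 = 75.0% vs 60.0% | 80/80 = 100% vs 80.0% |

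Across 70% to 90% response at entry and 5 to 30 leavers, the gap runs from 3.4 points (65/95 against 65/100) to 30 points (70/70 against 70/100).

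**Direction depends on who leaves.** Take 12 leavers. If all 12 had lost response, the observed rate is 68/88 = 77.3%, so a fall from 80% is visible, against 68.0% under the failure rule. If 5 had lost response and 7 never responded, the observed rate is 75/88 = 85.2%, an apparent rise, against 75.0%.

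**Prohibited therapy.** Each participant who responds after starting one and stays on study adds 1/n to the observed rate among the n assessed. The failure rule removes it.

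**Administrative exits.** Protocol 6.1 ends LTE treatment on turning 18 where adult use is approved (with the opportunity for up to a year in the LTE), on paediatric approval or denial, or on a company decision. Assume 20 efficacy exits by former responders, leaving 60 responders among 80, then 30 administrative exits unrelated to response. Responders remaining are 60 × (1 − 30/80) = 37.5 among 50.

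- Observed: 37.5/50 = 75.0%
- Failures carried forward without limit: 37.5/(50 + 20) = 53.6%
- Non-responder imputation for everyone absent: 37.5/100 = 37.5%
- Failures counted only until they too would have left administratively, at the same 30/80 rate: 20 × 50/80 = 12.5, giving 37.5/62.5 = 60.0%

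The last figure equals the failure-rule rate with no administrative exits (60/100).

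**Entry.** If 75 of 100 Week 52 completers respond (assumed), the LTE starts at 75.0% when all enter. It starts at 75/90 = 83.3% or 75/85 = 88.2% if 10 or 15 non-responding completers do not.

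**Text check.** The Week 60 and Week 84 retreatment summaries fall under two consecutive paragraphs of SAP 5.1.3.6, one keeping the failure rule and one dropping it. The LTE schedule has PASI, IGA and BSA at Week 60, every 24 weeks and at completion or termination, so a participant can fail and leave between scheduled efficacy visits.

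**The case against.** Observed-case summaries are a legitimate description of participants still on treatment, and the plan does not conceal exits. SAP 4.2 summarises LTE discontinuations with reasons and lists participants who met treatment-failure criteria. SAP 4.5 summarises disallowed concomitant treatment as a major deviation through the end of study. Starting a prohibited therapy normally means stopping study intervention. The LTE termination visit includes IGA, PASI and BSA, so some data after failure are collected. LTE efficacy is descriptive and outside the tested hierarchy. Replacing the observed summary with failures carried forward would bias the other way, because failures accumulate while responders leave administratively (53.6% against 60.0% above).

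Most of this stands and limits the point. It does not remove it: disposition tables and listings do not correct the response rates, and the SAP does not say how the termination visit enters the by-visit tables.

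Two stronger readings are tempting and not supported. A reader might infer that LTE response will look maintained whatever happens, or that loss of response cannot show. In fact, anyone still assessed who loses response counts as a non-responder, and the 77.3% example shows a visible fall. A reader might also infer that the two entry descriptions leave the analysis set undefined. Protocol 4.1 defers to Section 8 for detail, and the LTE set is whoever actually entered, so this is a wording mismatch that affects how the starting rate is read.

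**Conclusion.** The point holds in conditional form. If participants stop for lack of efficacy or worsening psoriasis, or start a prohibited therapy and stay on study, LTE response rates are selected upward relative to the Week 52 rates they extend, and no planned analysis shows by how much.

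The size rests on the number and type of efficacy-related exits, which the documents do not give. It is zero with none, and 3.4 to 30 points over the assumed ranges. A decline may still appear in part. Week 16 and Week 52 conclusions are untouched. This is a cheap improvement.

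**What to change.** In SAP 5.1.3.6, 5.5.2.3 and 5.5.3:

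1. Keep the observed-case LTE summary, label it as such, and show n at each visit.
2. Add a supplementary LTE summary applying SAP 5.1.3.2 and 5.1.3.3 to discontinuation for lack of efficacy or worsening psoriasis and to therapies still prohibited after Week 52, but not to topicals that Protocol 6.5.5 permits. Leave other missing data unimputed.
3. In that summary, count a failed participant as a non-responder only through visits that participant could have reached before an administrative exit (age 18, approval, denial, company decision).
4. State which rule governs the Week 60 and Week 84 retreatment summaries, and reconcile SAP 5.1.3.5 with 5.1.3.6 for the LTE.
5. Reconcile the LTE entry wording of Protocol 4.1 and SAP 1.2 with that of the synopsis and Protocol 6.1 and 8. Report how many Week 52 completers did not enter and why.

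The cost is SAP and protocol wording, a little more analysis that reuses existing derivations, and LTE rates that look somewhat less favourable.

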5.2. Primary Efficacy Endpoints

5.2.1. Definition

There are 2 co-primary endpoints in this study: the proportion of subjects who achieve an IGA score of cleared (0) or minimal (1) at Week 16 and the proportion of subjects who achieve a PASI 75 response at Week 16. Refer to Section 5.1.2.1 and 5.1.2.2 for the definition of IGA and PASI responses.

5.2.2. Primary Estimand

The composite estimand assesses the treatment effects not only based on the variable measurements, but also based on intercurrent event defined in TF criteria and rescue treatment criteria. If a subject had to use rescue medication or meet TF criteria, the subject will be a non-responder for co-primary endpoints. This estimand acknowledges that subjects meeting the TF criteria or using rescue treatment have an unfavorable outcome.

Population: subjects with chronic plaque psoriasis who are randomized to guselkumab or placebo in Part 1 of the study.

Variable: the endpoint is defined as proportion of subjects who achieve an IGA score of cleared (0) or minimal (1) at Week 16 or the proportion of subjects who achieve a PASI 75 response at Week 16. Non-responder status is assigned after meet TF or rescue treatment criteria.

Intercurrent Events: the intercurrent event is captured through the variable definition.

Population-level summary: difference in response proportions between guselkumab group and placebo group.

5.2.3. Analysis Methods

These 2 co-primary endpoints will be compared between the guselkumab group and the placebo group. In these primary efficacy analyses, data from all randomized subjects will be analyzed according to their assigned treatment group (ie, full analysis set). The number and proportion of subjects who achieve an IGA score of cleared (0) or minimal (1) and a PASI 75 response at Week 16 will be summarized for each treatment group respectively. The differences in proportions between guselkumab and placebo treatment groups with exact 95% confidence intervals will also be presented.

To address the primary objective, a 2-sided ($\alpha=0.05$) Fisher's exact test, stratified by age group (≥ 6 to <12 years, ≥ 12 to <18 years) and pooled region (NA, EU), will be used for the co-primary endpoints. The study will be considered positive if the guselkumab group is significantly different from the placebo group for both co-primary endpoints. Both co-primary endpoints will be tested at a 2-sided α -level of 0.05. If one of the comparisons is not significant, the co-primary endpoints will be considered not significant.

In addition, the comparison between etanercept and placebo for the co-primary endpoints will be performed using Fisher's exact test, stratified by age and region, and nominal p-values will be reported.

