#### **9.4.1.3. Primary Analysis**

There are 2 primary estimands corresponding to the 2 co-primary endpoints in this study for participants randomized in Part 1 of this study: the proportion of participants who achieve an IGA score of cleared (0) or minimal (1) and the proportion of participants who achieve a PASI 75 response at Week 16. These 2 co-primary endpoints will be compared between the guselkumab group and the placebo group. In the primary efficacy analysis, data from all randomized participants will be analyzed according to their assigned treatment group. Participants who meet treatment failure criteria or initiate use with a low to high potency topical steroid as rescue treatment before Week 16 will be considered nonresponders for the primary endpoints at Week 16. In addition, participants who do not return for evaluation at Week 16 will be considered nonresponders at Week 16.

To address the primary objective, a 2-sided ( $\alpha=0.05$ ) Fisher's exact test, stratified by age and region, will be used for the co-primary endpoints. The exact 95% confidence interval for treatment difference between guselkumab and placebo treatment groups will be provided.

The study will be considered positive if the guselkumab group is significantly different from the placebo group for both co-primary endpoints. If one of the comparisons is not significant at the 2-sided  $\alpha$ -level of 0.05, the co-primary endpoints will be considered not significant.

In addition, the comparison between etanercept and placebo for the co-primary endpoints will be performed and nominal p-values will be reported.

Subgroup analyses will be performed to evaluate consistency of the co-primary endpoints over demographics (including baseline weight), baseline disease characteristics and prior medications. Sensitivity analyses and per-protocol analysis will be performed for the co-primary endpoints and will be documented in the SAP.

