1.2. Trial Design

This is a Phase 3, multicenter, randomized, placebo- and active comparator-controlled study evaluating the efficacy, safety, and PK of subcutaneously administered guselkumab for the treatment of chronic plaque psoriasis in pediatric participants ≥ 6 to < 18 years of age. The participant population will be comprised of boys and girls who have had a diagnosis of chronic plaque-type psoriasis, defined as having an Investigator's Global Assessment (IGA) ≥ 3 , a Psoriasis Area and Severity Index (PASI) ≥ 12 , a $\geq 10\%$ body surface area (BSA) involvement, and at least one of the following: very thick lesions, clinically relevant facial, genital, or hand/ foot

involvement, PASI ≥ 20 , $>20\%$ BSA involvement, or IGA=4. Participants must also be a candidate for phototherapy or systemic treatment of plaque psoriasis and have plaque psoriasis considered by the investigator as inadequately controlled with phototherapy and/or topical therapy after an adequate dose and duration of therapy.

The main study will be conducted in 2 parts. In Part 1, the efficacy, safety, and PK of guselkumab will be evaluated in pediatric participants during a 16-week randomized, placebo- and active comparator-controlled period followed by an uncontrolled period of withdrawal and retreatment or initiation of treatment with guselkumab through Week 52.

Part 1 of the study will be divided into Part 1a (≥ 12 to <18 years of age [ie, adolescents]) and Part 1b (≥ 6 to <12 years of age) and enroll a minimum of 90 participants. Part 1a will enroll at least 60 participants randomized in a 2:1:1 ratio to guselkumab (n=30), placebo (n=15), and etanercept (n=15). Part 1b will enroll at least 30 participants randomized in a 1:1:1 ratio to guselkumab (n=10), placebo (n=10), and etanercept (n=10). Enrollment of participants ≥ 6 to <12 years of age in Part 1b will commence only after:

- 1) All participants ≥ 12 to <18 years of age in Part 1a will have completed Week 16, and all available safety data have been reviewed by an independent Data Monitoring Committee (DMC), with no important safety concerns identified.
- 2) All available guselkumab PK data for the ≥ 12 to <18 -year-old participants through Week 16 have been evaluated to determine if the body weight-based dose used in Part 1a has provided systemic exposure comparable to adults, or whether a revised body weight-based dose should be instituted in Part 1b.

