5.2.5. Sensitivity Analysis

To assess the robustness of the co-primary endpoint analysis results, two sensitivity analyses will be conducted for the co-primary endpoints as specified below.

Sensitivity Analysis 1

For subjects who have missing IGA or PASI score at Week 16, the score will not be imputed. That is, the Fisher's exact test, stratified by age group and region, will be used for the co-primary endpoints will be performed using observed data after applying treatment failure rules (as defined in Section 5.1.3.2) and rescue treatment rules (as defined in Section 5.1.3.5).

Sensitivity Analysis 2

The second sensitivity analysis will be performed using multiple imputations by fully conditional specification (MI FCS), after applying treatment failure rules (as defined in Section 5.1.3.2) and rescue treatment rules (as defined in Section 5.1.3.5). The missing data of the IGA score of 0/1 and PASI 75 responses will be imputed with FCS logistic regression with treatment group, region, and age group in the model with 500 imputation and seed =36789. The proportion of IGA score of 0/1 and PASI 75 responses at Week 16 will be compared between the guselkumab and the placebo group combining the Mantel-Haenszel estimates stratified by region and age group obtained from the multiple imputation datasets using PROC MIANALYZE.

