5.3.3. Analysis Methods

For categorical response parameters (PASI 90, IGA score of 0, PASI 100 response) at Week 16, the Fisher's exact test, stratified by age group and region, will be used to compare the proportion of participants responding to treatment between the guselkumab and placebo group. The p-values and the differences in proportions with exact 95% confidence intervals will be presented.

The change from baseline in CDLQI at Week 16 will be analyzed using a Mixed Model for Repeated Measures (MMRM) model to test the difference between treatment groups and adjust for missing data. The independent variables for this model may include treatment group (guselkumab, placebo, and etanercept), region (NA, EU), age group (6 - <12 years, 12- <18 years), baseline CDLQI score, visit week, an interaction of baseline CDLQI score and visit, and an interaction of treatment and visit as appropriate. An unstructured (UN) variance-covariance matrix for repeated measures within a subject will be used. The treatment difference between guselkumab and the placebo group will be estimated by difference in LSmeans. The 95% CIs for difference in LSmean between the groups and p-values will be calculated.

In addition, the comparison between etanercept and placebo for the major secondary endpoints will be performed and nominal p-values will be reported.

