5.4.2. Analysis Methods

For US-FDA specific primary and major secondary endpoints, the proportion of participants responding to treatment will be compared between the guselkumab and placebo group in the same manner as the global primary and major secondary endpoints. Table 5 presents the differences between the US-FDA specific primary and major secondary endpoints to the global endpoints. The same endpoints are not listed.

Table 5: Differences between US-FDA specific primary and major secondary endpoints to global endpoints		
	Global endpoints	US-FDA specified endpoints
Co-primary	PASI 75 response at Week 16 is one of the co-primary endpoints.	PASI 90 response at Week 16 is one of the co-primary endpoints.
Major secondary	PASI 90 response at Week 16 is the first major secondary endpoint.	PASI 75 response at Week 16 is the first major secondary endpoint.
Analysis methods	Fisher's exact test, stratified by age group and pooled region, will be used to compare the PASI 90 and PASI 75 response rates between treatment groups.	Same
Sensitivity analyses	
 Observed data after apply TF and rescue treatment rule. Multiple imputation with FCS logistic regression. 	Same

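### The reported response difference and its exact CI name no age strata, although the planned arms differ in age mix (75% versus 60% adolescent); an age-stratified main estimate would be a small, cheap improvement

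*SAP*

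**What the plan says.** SAP 5.2.3 compares guselkumab with placebo on the two co-primary responses by a two-sided Fisher test stratified by age group and pooled region. The effect size has its own sentence: "The differences in proportions between guselkumab and placebo treatment groups with exact 95% confidence intervals will also be presented". Protocol 9.4.1.3 is worded similarly: "The exact 95% confidence interval for treatment difference between guselkumab and placebo treatment groups will be provided". For the binary major secondary endpoints SAP 5.3.3 again stratifies the test and then adds: "The p-values and the differences in proportions with exact 95% confidence intervals will be presented". SAP 5.4.2 carries this over to both tiers of the US-FDA set: "the proportion of participants responding to treatment will be compared between the guselkumab and placebo group in the same manner as the global primary".

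The estimands in SAP 5.2.2 and 5.3.2.1 share one summary line: "Population-level summary: difference in response proportions between guselkumab group and placebo group". It gives no strata or weights.

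SAP 1.2 plans at least 60 adolescents in Part 1a at 2:1:1 (30 guselkumab, 15 placebo, 15 etanercept) and at least 30 children aged 6 to under 12 in Part 1b at 1:1:1 (10 per arm). SAP 1.5.1 says the two parts are randomized separately.

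A stratified effect estimate does appear once, in Sensitivity Analysis 2 of SAP 5.2.5, by "combining the Mantel-Haenszel estimates stratified by region and age group obtained from the multiple imputation datasets using PROC MIANALYZE". Table 4 in SAP 5.3.5 extends it to the binary major secondaries and Table 5 in SAP 5.4.2 to the US-FDA set.

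**The concern.** Pooling two separately randomized cohorts with different allocation ratios gives arms whose age mix differs by design. Unlike a chance imbalance, this does not average out. If response differs between the cohorts, a crude difference mixes that with the treatment effect.

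A cohort difference need not come from age alone. Part 1b starts only after Part 1a has reached Week 16, and SAP 1.2 allows a revised weight-based dose for it.

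What is at stake is the headline effect size for the binary co-primary and major secondary endpoints, not the test. The stratified estimate already planned does not fully fill the gap, because Sensitivity Analysis 2 also replaces non-responder imputation with multiple imputation. If it differed from the headline figure, a reader could not tell age weighting from missing-data handling.

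**Working it through.** **Inputs.** From SAP 1.2 and 1.4: guselkumab 30 + 10 = 40, placebo 15 + 10 = 25, with response 65% versus 13% as the conservative case. Age gaps in response (adolescents minus children) are assumptions; the documents give none.

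**The plan's own figures.** Full enumeration of the unstratified two-sided Fisher test gives power of 99.3% at 65% versus 13% (stated: above 99%). For etanercept it gives 81.0%, 84.9% and 92.4% (stated: 81%, 85%, 92%). The power tables reproduce.

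**Age mix.** Guselkumab 30/40 = 75% adolescent; placebo 15/25 = 60%. Etanercept versus placebo is balanced (15 + 10 in each arm) and not affected.

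**MH weights.** Each stratum has weight n1 × n2/(n1 + n2). Adolescents: 30 × 15/45 = 10. Children: 10 × 10/20 = 5. The shares are 2/3 and 1/3.

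**Shift.** With gaps G on guselkumab and P on placebo, crude minus MH = (0.75 − 0.667) × G + (0.667 − 0.60) × P = 0.083 × G + 0.067 × P.

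| Assumed gap, overall rates 65% vs 13% | Crude | MH | Shift (points) |
|---|---|---|---|
| None | 52.0 | 52.0 | 0 |
| 10 points, guselkumab only | 52.0 | 51.2 or 52.8 | 0.8 |
| 10 points, both arms | 52.0 | 50.5 or 53.5 | 1.5 |
| 20 points, both arms | 52.0 | 49.0 or 55.0 | 3.0 |

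The first MH value applies if adolescents respond more, the second if children do.

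**PASI 90.** Take the adult rates in Protocol 2.2.1 (73.3% versus 2.9%). The placebo gap cannot exceed 2.9/0.60 = 4.8 points (adolescents higher) or 2.9/0.40 = 7.25 points (children higher). With a 20-point guselkumab gap the shift is at most 0.083 × 20 + 0.067 × 4.8 = 2.0 points, or 0.083 × 20 + 0.067 × 7.25 = 2.15 points. The sample-size sections give no rates for IGA 0 or PASI 100.

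**Against sampling error.** The crude SE is √(0.65 × 0.35/40 + 0.13 × 0.87/25) = 0.101, a half-width of about 19.8 points. A shift of 1.5 points is 0.15 SE; 3.0 points is 0.30 SE.

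**Does the crude exact interval still cover the MH difference?** Two unstratified exact unconditional intervals were enumerated at 65% versus 13%, with equal gaps of 0, ±10 and ±20 points in both arms.
- Inverting tests on the raw difference: coverage 96.7% to 97.1%.
- Inverting the score statistic: coverage 95.2% to 96.3%.
- At 20-point gaps one tail exceeds 2.5%: 2.7% or 3.1% if adolescents respond more, 3.0% or 4.1% if children do.
- In the PASI 90 scenarios: 98.1% to 98.5% and 96.0% to 96.3%.

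**Candidate stratified intervals.** These were enumerated by age stratum at the planned sizes. In the same 65% versus 13% scenarios a stratified Miettinen-Nurminen interval covers 94.9% to 95.3% and an MH Wald interval 92.8% to 93.4%. In the PASI 90 scenarios with a 20-point guselkumab gap the figures are 96.2% to 96.6% and 92.3% to 93.2%.

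**Why the weights need naming.** With equal gaps in both arms the shift is 0.15 × gap under any common weights. With a 20-point gap on guselkumab only it depends on the target: 1.7 points against MH weights, 1.2 against the pooled two-arm mix, 0 against the guselkumab mix and 3.0 against the placebo mix.

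**The case against.** The strongest reply has four parts.

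1. The text is silent; it does not say unstratified. The neighbouring paragraph stratifies the comparison, so a stratified interval could have been intended. This stands as a limit on the wording of the point. But if a stratified interval was meant, nothing identifies it.

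2. The documents contain no age effect. Protocol 4.3 chose weight-based dosing to give similar exposure across ages, so the shift may be nil. The both-arms case is also demanding: with 13% on placebo overall, a 10-point gap means 17% versus 7%, and a 20-point gap 21% versus 1%. This stands. The size is conditional and the range includes zero.

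3. Much is already planned. There is the stratified MH estimate in Sensitivity Analysis 2, and SAP 2.5 and 5.2.6 give age-specific differences with exact intervals for the co-primaries. This stands in part. No combined stratified estimate is planned under the primary missing-data rule, and the subgroup tables do not extend to the major secondaries.

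4. A crude difference with an exact interval is a defensible choice with only 10 per arm in Part 1b, because its coverage is guaranteed for the crude difference. This stands as a cost of changing.

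A reader might go further and infer that the superiority test, or the validity of the interval, is compromised. The documents do not support that. The test is stratified by age group and region, and the crude exact interval kept at least 95% two-sided coverage of the MH difference in every scenario computed.

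**Conclusion.** The point holds as a minor one. On its plain reading the plan reports a crude difference between arms that differ by 15 percentage points in adolescent share by design, while the accompanying test is age-stratified. The departure from the MH difference is 0 to 3.0 points over the assumed gaps shown, in either direction, or up to about 0.30 SE.

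This rests on the planned minimum enrolments, so actual shares may differ, and on assumed age gaps. It would be too strong to say that the headline estimate is biased: that requires an age or cohort effect, which the documents do not report.

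**What to change.** - In SAP 5.2.3 and 5.3.3 (and so 5.4.2) and Protocol 9.4.1.3, report as the main effect for the binary co-primary and major secondary endpoints the MH risk difference stratified by age group, under the primary non-responder imputation.
- Give it a stratified Miettinen-Nurminen score interval. Exclude the MH Wald interval, which covers only about 93% at these sizes.
- Stratifying by region as well is optional. The ratio is constant across regions within each part, so age group alone removes the planned imbalance.
- State the weights in the summary lines of SAP 5.2.2 and 5.3.2.1.
- Keep the crude proportions and exact interval as descriptive, and name the exact method.

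The cost is SAP and protocol wording and a few lines of code. The main interval becomes approximate, with coverage of about 95% that is not guaranteed. It may disagree with the stratified Fisher p-value in borderline cases. Precision changes little: at 65% versus 13% the MH standard error is 0.1025 with no gap, 0.1043 to 0.1045 if adolescents respond more and 0.099 to 0.094 if children do (gaps of 10 and 20 points in both arms), against 0.101 for the crude difference.
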